8.4 Handling missing or partial medication dates (rescue insulin only)

In order to select the date of rescue medication initiation and to derive the total daily dose of rescue insulin, partial start and stop dates will be imputed as follows:

- For partial start dates:
 - Calculate a surrogate date as the first rescue visit start date. If there is no available rescue visit start date, the surrogate date will be set to missing.
 - Based on the information provided, set the derived date to the earliest possible date. If only the year is provided, impute onset date as 1st January of that year. If the year and month are provided, impute onset date as 1st day of that month and year.
 - If the surrogate date is non-missing then:
 - i. If the derived date is on or after the surrogate date, use the derived date as calculated
 - ii. If the derived date is prior to the surrogate date, then use the surrogate date as the derived date.
 - If the surrogate date is missing, then use the derived date.
- For partial stop dates:
 - If only the year is provided, impute stop date as 31st December of that year, or end of study date for that subject or death date, whichever is earlier.
 - If the year and month are provided, impute stop date as the last day of that month and year, or end of study date for that subject or death date, whichever is earlier.

Imputed dates will not appear on the listings of non-study medication.

8.5 Handling missing or partial T2DM diagnosis dates

If the T2DM diagnosis date is partially missing, the following rules will take effect:

- Missing day, but month and year are present: the day will be imputed as the 15th day of the month, or date of informed consent, whichever is earlier.
- Missing day and month, but year is present: the day and month will be imputed as 30 June of the year, or date of informed consent, whichever is earlier.
- Missing year, but day and month are present: No imputations will occur, and the subject will be excluded from all summaries related to duration of T2DM.

- Missing day, month and year: No imputations will occur, and the subject will be excluded from all summaries related to duration of T2DM.

If any such imputed date falls after the informed consent date, then the diagnosis date will be taken as equal to the informed consent date.

8.6 Deriving age at each visit

8.6.1 Age used to derive normalised height, body weight and BMI expressed as z-score

For baseline assessment, age at the time of the assessment used for baseline will be used. At Week 6, Week 12, Week 20, Week 26, Week 32, Week 40, Week 52, premature end of treatment visit, non-treatment follow-up visit, and Week 104 the age (months) will be derived as:

$(\text{Visit date} - \text{birth date} + 1) / 30.5;$

If only year part of date of birth is available, this will be imputed to 30th of June. If imputed date of birth results in the derived age being less than the IWRS age at screening, then use IWRS age.

8.7 Clinical laboratory variables

8.7.1 Marked abnormality criteria for safety laboratory variables

Clinical laboratory variables will be summarised and listed using the units listed here. The criteria for marked abnormality for each variable are listed in the following table. Note that a post-baseline laboratory value will be considered a MA only if it satisfies the specified criteria as described in Section 4.7.3.4.

Table 18 Marked laboratory abnormalities

Conventional (US) Units:

Clinical Laboratory variables	Units	Marked Abnormality Criteria	
		Low	High
Hematology			
Haematocrit	%	< 20.0%	> 55.0%
Haematocrit	%		> 60.0%
Haemoglobin	g/dL	< 6 g/dL	> 18 g/dL
Haemoglobin	g/dL		> 20 g/dL
Blood Chemistry			
Protein, total	g/dL		> 10 g/dL
ALP	U/L		> 3X ULN
ALT	U/L		> 3X ULN
AST	U/L		> 3X ULN
ALT	U/L		> 5X ULN
AST	U/L		> 5X ULN
ALT	U/L		> 10X ULN
AST	U/L		> 10X ULN
ALT	U/L		> 20X ULN
AST	U/L		> 20X ULN
Bilirubin, total	mg/dL		> 1.5X ULN if PreTx ≤ ULN
Bilirubin, total	mg/dL		> 2X ULN if PreTx > ULN
Glucose, Plasma Unspecified	mg/dL	< 54 mg/dL	> 350 mg/dL
Na (Sodium)	mEq/L	< 130 mEq/L	> 150 mEq/L
Na (Sodium)	mEq/L	< 120 mEq/L	
K (Potassium)	mEq/L	≤ 2.5 mEq/L	≥ 6.0 mEq/L
Creatinine	mg/dL		≥ 1.5X PreTx CREAT
Creatinine	mg/dL		≥ 2.5 mg/dL
Calcium	mg/dL	< 7.5 mg/dL	≥ 1 mg/dL from ULN and ≥ 0.5 mg/dL from PreTx CA
Magnesium	mEq/L	< 1 mEq/L	> 4 mEq/L
PO4 (Phosphate)	mg/dL	Age 17-65: ≤ 1.8mg/dL	Age 17-65: ≥ 5.6 mg/dL
Urine			
UACR (Urinary Albumin to Creatinine Ratio)	mg/g		> 1800 mg/g

Standard International Units

Clinical Laboratory variables	Units	Marked Abnormality Criteria	
		Low	High
Hematology			
Haematocrit	ratio	< 0.20	> 0.55
Haematocrit	ratio		> 0.60
Haemoglobin	g/L	< 60 g/L	> 180 g/L
Haemoglobin	g/L		> 200 g/L
Blood Chemistry			
Protein, total	g/L		> 100 g/L
ALP	ukat/L		> 3X ULN
ALT	ukat/L		> 3X ULN
AST	ukat/L		> 3X ULN
ALT	ukat/L		> 5X ULN
AST	ukat/L		> 5X ULN
ALT	ukat/L		> 10X ULN
AST	ukat/L		> 10X ULN
ALT	ukat/L		> 20X ULN
AST	ukat/L		> 20X ULN
Bilirubin, total	µmol/L		> 1.5X ULN if PreTx ≤ ULN
Bilirubin, total	µmol/L		> 2X ULN if PreTx > ULN
Glucose, Plasma Unspecified	mmol/L	< 3 mmol/L	> 19.4 mmol/L
Na (Sodium)	mmol/L	< 130 mmol/L	> 150 mmol/L
Na (Sodium)	mmol/L	< 120 mmol/L	
K (Potassium)	mmol/L	≤ 2.5 mmol/L	≥ 6.0 mmol/L
Creatinine	µmol/L		≥ 1.5X PreTx CREAT
Creatinine	µmol/L		≥ 221 µmol/L
Calcium	mmol/L	< 1.88 mmol/L	≥ 0.25 mmol/L from ULN and ≥ 0.13 mmol/L from PreTx CA
Magnesium	mmol/L	< 0.5 mmol/L	> 2 mmol/L
PO4 (Phosphate)	mmol/L	Age 17-65: ≤ 0.58 mmol/L	Age 17-65: ≥ 1.81 mmol/L
Urine			
UACR (Urinary Albumin to Creatinine Ratio)	g/mol		> 203.62 g/mol

Elevated AT (ALT and/or AST) and total Bilirubin

The following three criteria will be summarised in examination of elevated AT (ALT and/or AST) and total bilirubin:

- (AST or ALT > 3X ULN) and (Bilirubin > 1.5X ULN within 14 days on or after AT elevation),
- (AST or ALT > 3X ULN) and (Bilirubin > 2X ULN within 14 days on or after AT elevation),

- (AST or ALT > 3X ULN) and {(Bilirubin > 2X ULN and no ALP >= 2X ULN) within 14 days on or after AT elevation)}.

8.8 Subgroups

Table 19 Subgroups analyses

Group variable	Subgroups
Race	White Non-White
Ethnicity	Hispanic or Latino Not Hispanic or Latino
Sex*	Male Female
Subject age*	≥ 10 and < 15 years ≥ 15 and < 18 years
Baseline HbA1c	< 8% ≥ 8%
Geographic region	North America Latin America Europe Asia/Pacific
Antidiabetic background medication*	Metformin only Insulin only Metformin + Insulin
Baseline body mass index	< 30 kg/m ² ≥ 30 kg/m ²

* based on randomisation strata.

8.9 Classification of hypoglycaemia episodes

Table 20 Classification of hypoglycaemia episodes

Category	Derivation (based on CRF Hypoglycaemia page)
ADA Classification	
Glucose alert value. A glucose alert value of 70 mg/dl (3.9 mmol/l) or less.	Lowest blood glucose value ≤ 70 mg/dl (3.9 mmol/l) and must be not missing.

Category	Derivation (based on CRF Hypoglycaemia page)

Clinically important hypoglycaemia. A glucose level of < 54 mg/dl (< 3.0 mmol/l) is sufficiently low to indicate serious, clinically important hypoglycaemia.
	
Lowest blood glucose value < 54 mg/dl (3.0 mmol/l) and must be not missing.

Severe hypoglycaemia. Severe hypoglycaemia, as defined by the ADA (6,7), denotes severe cognitive impairment requiring external assistance for recovery.
	
"Was third party intervention required for this episode of hypoglycaemia?" must be Yes

ISPAD Classification	

Mild/moderate hypoglycaemia
 
The child or parent is aware of, responds to, and treats the hypoglycaemia orally after documenting a blood glucose level of ≤ 3.9 mmol/L (70 mg/dL), where the ADA has suggested using the terminology of 'Documented Symptomatic Hypoglycaemia' for this category.
 
Or the child is not symptomatic with hypoglycaemia but the blood glucose is documented to be ≤ 3.9 mmol/L (70 mg/dL), where the ADA has suggested using the terminology of 'Asymptomatic Hypoglycaemia' for this category.
	
EITHER:
 
["Any Symptoms?" must be Yes.
 
Lowest Blood Glucose Value ≤ 70 mg/dl (3.9 mmol/l) and must be not missing.
 
Required Treatment must be Yes, and the treatment must be "Oral Treatment" or "Glucose Treatment" only.]
 
OR
 
["Any Symptoms?" must be No.
 
Lowest Blood Glucose Value ≤ 70 mg/dl (3.9 mmol/l) and must be not missing.]

Severe hypoglycaemia
 
The child is having altered mental status and cannot assist in their care, is semiconscious or unconscious, or in coma± convulsions and may require parenteral therapy (glucagon or i.v. glucose).
	
"Any Symptoms?" must be Yes.
 
"Was third party intervention required for this episode of hypoglycaemia?" must be Yes.
 
"Required treatment" must be Yes.

8.10 Puberty status and height velocity used to categorise growth and maturation markers as well as bone biomarkers

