4.7.2.4 Hypoglycaemia

Hypoglycaemic events will be included in summaries for the ST, ST+LT and randomised withdrawal periods if their onset falls between the start of IP treatment and the cut-off dates defined for each period in [Table 8](#). The primary analysis will be based on data including

hypoglycaemia events occurring prior to rescue medication initiation; sensitivity analyses will include data after rescue medication initiation.

The number and proportion of subjects with hypoglycaemic events (including those reported as SAEs) will be tabulated in each treatment group by ADA and ISPAD categories (see Section 8.9) for:

- The ST period and the combined ST+LT period, prior to rescue medication initiation (as primary analyses).
- The ST period and the combined ST+LT period, regardless of rescue medication initiation (as sensitivity analyses).
- The combined ST+LT period, up to Week 32, prior to rescue medication initiation (as primary analyses).
- The combined ST+LT period, up to Week 32, regardless of rescue medication initiation (as sensitivity analyses).
- The randomised withdrawal period. The events, with a date onset occurring on or after the randomised withdrawal prior to rescue medication initiation, will be summarised separately for the three treatment comparisons described in Section 4.1.5 using the Randomised Withdrawal Subjects Data Set.

The ST+LT period prior to rescue medication initiation analysis will also be repeated for the subgroup of subjects on a stable baseline dose of metformin IR or XR (with or without insulin).

Hypoglycaemic events that do not fulfil the ADA or ISPAD categories will be presented as ‘Not classified’.

All information (symptoms, risk factors etc.) collected in the separate CRF pages for hypoglycaemic events (whether or not they fulfilled SAE criteria) will be summarised by treatment group and listed for the ST+LT period. For the ST+LT + Week 104 period, the listing will include all data collected up to Week 104.

Hypoglycaemic events meeting SAE criteria will also be presented in the listing.

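### SAP Table 20 gives a symptomatic, glucose-confirmed but untreated hypoglycaemic episode no ISPAD grade, and lets an orally treated episode with third-party intervention meet both ISPAD grades

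*SAP*

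**What the plan says.** SAP Section 8.9, Table 20 sets a definition beside a CRF-based derivation for each category.

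- **ISPAD mild/moderate, definition.** The symptomatic part reads "The child or parent is aware of, responds to, and treats the hypoglycaemia orally after documenting a blood glucose level" of 70 mg/dL or less. A second part covers the asymptomatic child with a documented value in the same range.
- **ISPAD mild/moderate, derivation.** There are two routes. One needs symptoms, lowest glucose at or below 70 mg/dL, and "Required Treatment must be Yes, and the treatment must be" oral or glucose treatment only. The other needs no symptoms and lowest glucose at or below 70 mg/dL, with no condition on treatment.
- **ISPAD severe, definition.** "The child is having altered mental status and cannot assist in their care", or the child is semiconscious, unconscious or in coma, with or without convulsions.
- **ISPAD severe, derivation.** Symptoms Yes, third-party intervention required Yes, treatment required Yes. Mental status, treatment route and glucose are not tested.
- **ADA rows.** Glucose alert needs only "Lowest blood glucose value ≤ 70 mg/dl (3.9 mmol/l) and must be not missing". Clinically important needs a value below 54 mg/dL. Severe needs third-party intervention Yes.

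SAP Section 4.7.2.4 tabulates the number and proportion of subjects by ADA and ISPAD category and adds: "Hypoglycaemic events that do not fulfil the ADA or ISPAD categories will be presented as" *Not classified*.

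**The concern.** Hypoglycaemia is a named safety objective (protocol Section 1.3.3), and protocol Section 5.3.1.2 commits the study report to both ADA and ISPAD classification. Non-serious episodes are kept off the adverse event page (protocol Section 5.3.1.2, SAP Section 3.4.3.2), so no adverse event intensity grade stands behind Table 20.

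Two features of the ISPAD rules are hard to defend. First, adding symptoms to an untreated low glucose value takes the episode out of mild/moderate, which reverses the ordering a reader expects. Secondly, the two grades are not mutually exclusive. The mild/moderate definition expressly includes treatment by a parent, its derivation does not restrict third-party intervention, and the severe derivation does not ask for the mental-status change that separates the two definitions. In a population that includes 10-year-olds, help from a parent is foreseeable. The ISPAD rows would then be difficult to interpret, and two programmers could count the same episode differently.

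**Working it through.** The plan states no figure to reproduce, so the check is to apply Table 20 literally to every possible set of answers.

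**Inputs** (items collected separately on the hypoglycaemia CRF pages, SAP Section 3.4.3.2):

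- symptoms: yes, no (2)
- lowest glucose: below 54, 54 to 70, above 70 mg/dL, missing (4)
- third-party intervention: yes, no (2)
- treatment: none, oral or glucose only, other including parenteral (3)

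That gives 2 × 4 × 2 × 3 = 48 patterns.

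**Rules**

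- Mild/moderate = (symptoms and glucose ≤ 70 and oral/glucose only) or (no symptoms and glucose ≤ 70).
- Severe = symptoms and third party and any treatment.

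**Result over all 48 patterns:** 26 no ISPAD grade, 14 mild/moderate only, 6 severe only, 2 both (26 + 14 + 6 + 2 = 48).

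**Patterns with glucose ≤ 70 mg/dL** (each line covers the two glucose bands, below 54 and 54 to 70):

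| Symptoms | Treatment | Third party | ISPAD grade | Patterns |
|---|---|---|---|---|
| Yes | None | No | None | 2 |
| Yes | None | Yes | None | 2 |
| Yes | Oral/glucose only | No | Mild/moderate | 2 |
| Yes | Oral/glucose only | Yes | Both | 2 |
| Yes | Other | No | None | 2 |
| Yes | Other | Yes | Severe | 2 |
| No | Any of three | Either | Mild/moderate | 12 |

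The untreated symptomatic episode is ungraded in 4 of 4 patterns, while the asymptomatic one at the same glucose is mild/moderate in 12 of 12. The orally treated, third-party-assisted symptomatic episode meets both grades in 2 of 2. A further 2 symptomatic patterns (other treatment, no third party) are also ungraded.

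**ADA side.** All 24 patterns at or below 70 mg/dL meet the glucose alert row, and the 12 below 54 mg/dL also meet clinically important. None goes without an ADA category.

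**Is there a tie-break elsewhere?** The rule in SAP Section 3.4.1 that counts a subject once under maximum intensity is written for system organ class and preferred term tables, not for ISPAD grades. Neither Table 20 nor Section 4.7.2.4 states a hierarchy.

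These are counts of answer patterns, not of episodes; they say nothing about frequency.

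**The case against.** **The treatment condition follows the adopted definition.** The definition says the child or parent treats the episode, and the derivation implements that. This stands in part: the gap comes from the definition as quoted in the SAP as well as from the programming. The result is still that confirmed symptomatic episodes go ungraded while asymptomatic ones are graded.

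**The episode is not lost.** A reader might infer that it ends up as *Not classified*. The documents do not establish that. The episode meets at least one ADA row, and Section 4.7.2.4 does not say whether the label is applied per scheme or only when both schemes fail. The episode also stays within the overall line for at least one hypoglycaemia event (SAP Section 4.7.1.1) and in the summary and listing of hypoglycaemia CRF data. What is missing is the ISPAD grade.

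**The severe row need not be inflated.** A reader might infer that parent-assisted mild episodes will swell it. That depends on whether sites answer Yes to third-party intervention being required when a parent gives oral carbohydrate. The CRF completion rule is not in the documents. Table 20 permits the double count but does not show that it will happen.

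**Overlap is not an error in itself.** The ADA glucose rows are nested by construction. That is true, but the two ISPAD definitions describe different clinical states, so overlap there is not evidently intended.

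**Untreated episodes may be few.** Protocol Section 5.3.1.2 tells subjects to carry carbohydrate to treat an event. This is fair, and any percentage for the untreated share would have no basis in the documents.

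**Conclusion.** Read literally, Table 20 leaves a symptomatic, glucose-confirmed, untreated episode without an ISPAD grade, although the same glucose without symptoms is mild/moderate. It also lets one pattern satisfy both ISPAD grades, and its severe derivation omits the altered mental status in its definition. These are faults in a stated rule, not merely missing detail.

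The size in subjects cannot be computed, because the documents give no episode counts. For scale only, one subject in an arm of about 81 is 1/81 = 1.2 percentage points. Because the table counts subjects, someone with another graded episode would not leave the mild/moderate row.

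The consequence is confined to descriptive safety tables. The primary and hierarchical efficacy tests are untouched, and the same rule applies in every arm. The documents do not support the stronger conclusions that episodes disappear from the report or that severe hypoglycaemia will be overstated.

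**What to change.** 1. **Make the ISPAD grades mutually exclusive by testing severe first.** Keep the current severe derivation as the conservative default. If the hypoglycaemia CRF page codes altered consciousness, coma or convulsion, align the derivation with its definition and report the third-party-only version as a sensitivity tabulation. SAP Section 3.4.3.2 says symptoms are collected but does not list them, so this must be checked first.
2. **Close the gap.** Extend the symptomatic mild/moderate branch to glucose ≤ 70 mg/dL with no treatment, or with oral or glucose treatment only, when the episode is not severe. Alternatively, show symptomatic, confirmed, untreated episodes as a separate ISPAD row.
3. **State in SAP Section 4.7.2.4 that *Not classified* is applied separately for ADA and ISPAD.**

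With the default precedence and the extended branch, the 48 patterns become 26 − 4 = 22 ungraded, 14 + 4 = 18 mild/moderate, 6 + 2 = 8 severe and none in both.

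**Cost.** SAP wording and programming on items already collected. Mild/moderate counts may rise. The untreated branch goes slightly beyond the quoted definition, which speaks of treating the episode; the separate row avoids this. Under the default precedence, parent-assisted oral episodes with third party Yes stay in the severe row only. If severe is instead aligned with its definition, severe counts could fall, which is the less conservative direction for safety and the reason to keep the third-party-only tabulation beside it.

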8.10.1 Tanner staging

Table 21 Tanner staging criteria

Classification of Sex Maturity Stages in Girls		
Stage	Pubic Hair	Breasts
1	Preadolescent	Preadolescent
2	Sparse growth of long, slightly pigmented downy hair, straight or only slightly curled; appears chiefly along the labia	Breast bud stage; elevation of breast and papilla as a small mound; enlargement of areola diameter
3	Darker, beginning to curl, increased amount	Further enlargement of breast and areola with no separation of their contours
4	Resembles adult type but the area covered is still considerably smaller than in most adults; no spread to the medial surface of the thighs	Projection of areola and papilla form a secondary mound above the level of the breast
5	Adult in quantity and type, spread to medial surface of thighs	Mature; projection of papilla only due to recession of the areola to the general contour of the breast
Classification of Sex Maturity Stages in Boys		
Stage	Pubic Hair	Genitalia
1	None	Preadolescent
2	Sparse growth of long, slightly pigmented downy hair, straight or only slightly curled; appears chiefly at the base of the penis	Scrotum and testes have enlarged; change in texture of the scrotal skin with some reddening
3	Darker, coarser, and more curled; spreads sparsely over the junction of the pubes	Growth of the penis, mainly in length but with some increase in breadth; further growth of testes and scrotum
4	Resembles adult type but the area covered is still considerably smaller than in most adults; no spread to the medial surface of the thighs	Penis further enlarged in length and breadth with development of glans. Testes and scrotum further enlarged with further darkening of the scrotal skin
5	Adult in quantity and type, spread to medial surface of thighs	Adult size and shape. No further enlargement of testes and scrotum

8.10.2 Height velocity

The height velocity is defined as the change from baseline, or the previous measurement, to Week t in height (cm) standardised to 26 weeks (183 days) or 52 weeks (365 days). For example, change from Week 52 to Week 104.

The number of actual days between baseline, or the previous measurement, and Week t will be used to derive height velocity.

In case of missing Week t (Week 26, 52, or 104) height, an average change in height (in days) will be derived based on the actual day of the two closest non-missing observations (Week a and Week b, where Week a is the earlier of the two visits) to the planned visit. For missing Week 104, this will be the previous two observations collected. The average change in height per day will be multiplied by the number of days between the day of the Week a and Week t target date, and added to the height value of Week a to derive an imputed Week t value.

8.10.3 Puberty status

Puberty status will be defined, by visit, using the Tanner stage at that visit along with height velocity (as defined Section 8.10.1) as follow:

- Early/mid puberty: Tanner stage 1 or Tanner stage 2 or Tanner stage 3, or Tanner stage 4 with height velocity $\geq 1.5 \text{ cm}/26 \text{ weeks} = \geq 3 \text{ cm}/52 \text{ weeks}$,
- Late puberty and young adult: Tanner stage 4 with height velocity $< 1.5 \text{ cm}/26 \text{ weeks} = < 3 \text{ cm}/52 \text{ weeks}$, or Tanner stage 5.

8.11 Geographical regions

Table 22 Geographic Regions

Geographic Region	Countries
North America	Canada United States
Latin America	Argentina, Colombia Brazil, Mexico Chile
Europe	Ukraine, Russia Poland, Italy United Kingdom Finland, Romania Israel, Turkey
Asia/Pacific	Australia, Taiwan, Philippines, South Korea India, Thailand Malaysia, New Zealand

8.12 Reporting conventions

Reporting conventions will follow AZ's style guide, wherever applicable.

For summary statistics, the mean and median will be displayed to one decimal place greater than the original value and the measure of variability (e.g. SD, standard error [SE]) will be displayed to two decimal places greater than the original value. Minimum and maximum will be reported to the same decimal places as the original value. Least-square mean estimates will be rounded to two decimal places greater than the original value. Odds ratios will be rounded to one decimal place.

All values will be presented to a maximum 4 decimal places.

P-values ≥ 0.001 will be reported to three decimal places; p-values less than 0.001 will be reported as <0.001 . For frequency tabulations, percentages will be presented with one decimal place. Percentages less than 0.1% will be presented as '<0.1%'. If the frequency and percentage are zero they will be presented as '0' (instead of 0 (0.0)). Non-estimable SDs or SEs will be replaced with a dash ('-'). Confidence intervals will be reported to the same number of decimal places as the associated estimate. The nominal alpha defined for the study is 0.05 (two-sided).

